#### **Criteria for Group 5 (Placebo Only) Participants to Receive a Single Dose of $5 \times 10^{10}$ vp Ad26.COV2.S after EUA or Approval in any Country**

- Participants have to be actively enrolled in the study.
- Participants have not received an authorized/licensed COVID-19 vaccine outside of the study.
- Participants, who were already unblinded for any reason, might receive a single dose of  $5 \times 10^{10}$  vp Ad26.COV2.S vaccine at the investigator's discretion, provided they did not receive another licensed/authorized COVID-19 vaccine.
- Participants who have become infected with SARS-CoV-2 during the double-blind phase of the study may receive a single dose of  $5 \times 10^{10}$  vp Ad26.COV2.S vaccine after being made aware that the safety and efficacy data on vaccinating a previously infected individual is limited.
- Participants should not have previously experienced TTS, HIT, or GBS.
- Participant should not have previously experienced CLS

#### **Procedures for Group 5 (Placebo Only) Participants Receiving a Single Dose of $5 \times 10^{10}$ vp Ad26.COV2.S after EUA or Approval in any Country**

Participants who received placebo only during primary regimen accepting a single dose of  $5 \times 10^{10}$  vp Ad26.COV2.S, will discontinue from participation in the placebo groups (see Section [7.4](#)). They will be redirected to SoA 'Procedures for Group 5 (Placebo Only) Participants Receiving a Single Dose of  $5 \times 10^{10}$  vp Ad26.COV2.S (Placebo Crossover Vaccination) after EUA or Approval in any Country' (see Section [1.3.7](#)).

Vaccination will be planned during an ad hoc crossover visit as soon as the site is operationally ready. A urine pregnancy test will be collected from all women of childbearing potential (Cohorts 1 and 2) and a blood sample for a platelet count (as part of a complete blood count if applicable) will be collected from all participants prior to vaccination. Vaccination will be performed by a trained and qualified study nurse, medical doctor, or otherwise qualified HCP. Participants will remain under observation at the study site for at least 15 minutes for the presence of any acute reactions. SAEs, special reporting situations (whether serious or non-serious, that are related to study procedures or that are related to non-investigational sponsor products), and COVID-19-like signs and symptoms (refer to Section 8.1.2) will be reported from the time of unblinding until the end of safety follow-up/early withdrawal. In addition, AESIs will be reported after local approval of protocol Amendment 11 is obtained until the end of safety follow-up/early withdrawal. For Cohorts 1a, 1b, and 3, the safety follow-up will end at Day 422 (ie, the initially planned study completion date) or 6 months after vaccination, whichever comes first. For Cohorts 2a and 2b, the safety follow-up will end 6 months after vaccination. At that time, the participant will be contacted (phone call) by the site with regards to AESI and SAE collection, after which the participant will be considered to have completed the study.

## **8.7. Assessments and Procedures after Protocol Amendment 15 Approval (Ad Hoc Booster Vaccination)**

### **Ad Hoc Booster Vaccination**

Following local approval of protocol Amendment 15, all eligible participants will be offered a single ad hoc booster dose of  $5 \times 10^{10}$  vp Ad26.COV2.S.

As soon as possible, but no later than 120 days post local approval of protocol amendment 15, the ad hoc booster vaccination will be provided to participants who have previously received 1 or more doses of any COVID-19 vaccine (ie, the Ad26.COV2.S vaccine, an mRNA vaccine and/or another COVID-19 vaccine authorized for primary vaccination including protein, inactivated, and adenovector-based vaccines) if the last vaccination was  $\geq 6$  months ago. Participants are free to choose to delay the booster vaccination within the window of the booster vaccination visit, to receive booster vaccination outside the study, or not to receive booster vaccination. Participants who choose to receive an outside of the study booster vaccination with the Ad26.COV2.S vaccine (if recommended by local authorities and available) or another authorized COVID-19 vaccine, choose not to receive an ad hoc booster vaccination, or are not eligible to receive the ad hoc booster vaccination, will not be withdrawn from the study and will be encouraged to remain in the study.

Participants in Group 1 and 4 of Cohort 2 will be partially unblinded. See Section 6.3 for more details.

Participants will be counseled regarding the importance to continue practicing preventative measures to limit the spread of the disease including social distancing, wearing face masks, and frequent hand washing, in compliance with local and national guidelines. This contact will be documented in the source documents.

**Criteria for Participants Receiving a Single Ad Hoc Booster Dose of  $5 \times 10^{10}$  vp Ad26.COV2.S:**

- Participants have to be actively enrolled in the study.
- Participants have not received any COVID-19-related experimental medication (including any experimental vaccine other than the study vaccine).
- Participants who have become infected with SARS-CoV-2 during the study may receive booster vaccination with the Ad26.COV2.S vaccine after they have recovered from the acute illness and at least 3 months have passed. Such participants should be made aware that the safety and efficacy data on vaccinating a previously infected individual is limited.
- Participants should not have previously experienced TTS, HIT, or GBS.
- Participant should not have previously experienced CLS.
- Applicable to the US only: Participants who are pregnant may receive ad hoc booster vaccination with Ad26.COV2.S, if allowed by local regulations and if the investigator considers that the potential benefits outweigh the potential risks to the mother and fetus (see Section 8.7).

**Following ongoing participants will not be eligible to receive the ad hoc booster vaccination:**

Group 5 participants (all cohorts) who crossed over from placebo to receive Ad26.COV2.S at the  $5 \times 10^{10}$  vp dose level (ie, placebo crossover vaccination) (see Section 1.3.7).

Group 5 participants (all cohorts) who did not opt for the placebo crossover vaccination and therefore have not received any vaccination with the Ad26.COV2.S vaccine.

Cohort 2 participants who will receive a booster vaccination according to their initial schedule at 6 and 12 months after the primary regimen (Groups 2 and 3, respectively) (see Section 4.1).

Applicable to Belgium only: Per the Belgian-specific protocol Amendment 15, participants aged <65 years enrolled at Belgian sites.

**Procedures for Participants Receiving a Single Ad Hoc Booster Dose of  $5 \times 10^{10}$  vp Ad26.COV2.S**

Vaccination will be planned during the ad hoc booster vaccination visit as soon as the site is operationally ready and the participant has met the length of time requirements from last vaccination (see details above). During this visit, the investigator should ask the participant if he/she received any other COVID-19 vaccine and record type and date of administration.

A urine pregnancy test will be collected from all women of childbearing potential (Cohort 1 and 2 only) and a blood sample for a platelet count (as part of a complete blood count if applicable) will be collected from all participants prior to and 28 days post ad hoc booster vaccination. Vaccination will be performed by a trained and qualified blinded study nurse, medical doctor, or otherwise qualified HCP. Participants will remain under observation at the study site for at least 15 minutes for the presence of any acute reactions. Solicited AEs, collected through a diary, will be recorded from the time of ad hoc booster vaccination until 7 days post-vaccination. All other unsolicited AEs and special reporting situations, whether serious or non-serious, will be reported from the

time of ad hoc booster vaccination until 28 days post-vaccination. Unsolicited AEs with the onset date outside the timeframe of >28 days after previous study vaccination, which are ongoing on the day of the subsequent visit, should be recorded as such. SAEs and COVID-19-like signs and symptoms (refer to Section 8.1.2) will be reported from the time of booster vaccination till the end of booster follow-up/early withdrawal. In addition, AESIs will be reported until the end of booster follow-up/early withdrawal. At that time, the participant will visit the site with regards to AESI and SAE collection, after which the participant will be considered to have completed the study.

Venous blood samples will be collected for assessment of humoral or cellular immune responses from a subset of participants prior to and 28 days, and 6 months post ad hoc booster vaccination (see SoA in Section 1.3.10 for details).

## 9. STATISTICAL CONSIDERATIONS

Statistical analysis will be done by the sponsor or under the authority of the sponsor. A general description of the statistical methods to be used to analyze the efficacy and safety data is outlined below. Specific details will be provided in the Statistical Analysis Plan.

### 9.1. Statistical Hypotheses

No formal statistical hypothesis for safety or immunogenicity will be tested.

### 9.2. Sample Size Determination

The number of participants chosen for this study will provide a preliminary safety and immunogenicity assessment. Placebo recipients are included for blinding and safety purposes and will provide additional control specimens for immunogenicity assays.

While mild-to-moderate vaccine reactions (local site and systemic responses) are expected, AEs that preclude further dose administration or more serious ones that would limit product development are not anticipated. When 75 and 120 participants are vaccinated, the observation of 0 such reactions would be associated with a 95% confidence that the true rate is less than 3.9% and <2.5% respectively. Table 14 provides the probabilities of observing at least one AE at given true AE rates.

**Table 14: Probability of Observing at Least One Adverse Event Given a True Adverse Event Incidence**

True Adverse Event Incidence	Probability of Observing at Least One Adverse Event	
	N=75	N=120
1%	53%	70%
2.5%	85%	95%
5%	98%	>99%
10%	>99%	>99%
20%	>99%	>99%

N: number of participants receiving study vaccine (Ad26.COV2.S or a placebo).

### **9.3. Populations for Analysis Sets**

For purposes of analysis, the following populations are defined:

**FAS:** The full analysis set will include all participants with at least one vaccine administration documented.

**PPIa:** The per protocol immunogenicity population will include all randomized and vaccinated participants for whom immunogenicity data are available excluding participants with major protocol deviations expecting to impact the immunogenicity outcomes. In addition, samples obtained after missed vaccinations or from participants with natural infection occurring after screening (if applicable) will be excluded from the analysis.

**PPE:** The per protocol efficacy population will include all randomized participants having received at least 1 vaccination for whom efficacy data concerning endpoint measures are available. All efficacy analyses will be done according to the as treated principle (ie, actually received vaccinations).

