### **Populations for Analysis Sets**

For purposes of analysis, the following populations are defined:

FAS: The full analysis set will include all participants with at least one vaccine administration documented.

PPIa: The per protocol immunogenicity population will include all randomized and vaccinated participants for whom immunogenicity data are available excluding participants with major protocol deviations expecting to impact the immunogenicity outcomes. In addition, samples obtained after missed vaccinations or from participants with natural infection occurring after screening (if applicable) will be excluded from the analysis set.

PPE: The per protocol efficacy population will include all randomized participants having received at least 1 vaccination for whom efficacy data concerning endpoint measures are available. All efficacy analyses will be done according to the as treated principle (ie, actually received vaccinations).

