- Participants should complete the SIC (see Section 10.7, Appendix 7, Symptoms of Infection with Coronavirus-19 [SIC]) and record their highest body temperature daily starting on the first day they experience symptoms. If either nasal swab is positive for SARS-CoV-2 or influenza, collection of data will continue until sign and symptom resolution. If the first nasal swab is negative, collection of data will continue until the negative test is confirmed by the second nasal swab or until sign and symptom resolution, whichever comes first. Long-term sequelae of COVID-19 (eg, anosmia, headache, fatigue, and other symptoms at the investigator's judgement) will not be followed until their resolution if not resolved within a month.
- For participants with a positive test result for SARS-CoV-2 infection, a study visit will be conducted 28 days after symptom onset to assess the clinical course of the infection, record concomitant medications since symptom onset, and obtain a blood sample for assessment of the humoral immune response (VNA, ELISA, and Fc functionality) and other biomarkers (RNA-seq).

If a participant has a positive test result for SARS-CoV-2 infection, the participant may be requested to remain at home and not visit the study site. If necessary, study-site personnel will visit the participant at home. Under these circumstances, the participant will be contacted by the site at least once per week and the participant's medical care provider will be notified. The participant will not receive further study vaccinations but should remain on study for follow-up with assessments of safety and immunogenicity (see section 7.1), unless they withdraw consent from the study (see section 7.2). The participant will be followed until resolution of clinical symptoms (except for long-term sequelae of COVID-19).

The sponsor recommends to follow these participants until 2 consecutive negative nasal swabs could be obtained.

If a participant has a positive test result for influenza infection, study visits will continue per the [Schedule of Activities \(SoA\)](#).

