### **9.4.3. Secondary Endpoints**

#### **Immunogenicity Endpoints**

No formal hypothesis on immunogenicity will be tested. Descriptive statistics (geometric mean and 95% confidence interval, or median and interquartile range Q1-Q3, as appropriate) will be calculated for continuous immunologic parameters at all available time points. Graphical representations of immunologic parameters will be made as applicable. Frequency tabulations will be calculated for discrete (qualitative) immunologic parameters as applicable.

In addition, the ratio between neutralizing and binding antibodies as determined by VNA and S protein ELISA, respectively, will be calculated.

The immunogenicity analyses will be performed on the PPI population. Immunogenicity analyses will also be done on the FAS (participants who became infected during the study will be analyzed as a subgroup and shown in the graphs using different colors and symbols).

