## **9.7. Analyses after Unblinding all Participants Following EUA or Approval in any Country**

### **9.7.1. Cohorts 1a, 1b, and 3**

The participants in these cohorts have completed the planned study vaccination regimen by the time of unblinding (or have discontinued earlier). In general, after unblinding, participants who received placebo only during primary regimen, can elect to receive a single dose of

a Following local approval of protocol Amendment 15, participants who received an authorized/licensed COVID-19 vaccine outside of the study are allowed to receive a single ad hoc booster dose of Ad26.COV2.S vaccine ( $5 \times 10^{10}$  vp) if the last vaccination was  $\geq 6$  months ago.

$5 \times 10^{10}$  vp Ad26.COV2.S offered at the study site, can opt to receive an authorized/licensed COVID-19 vaccine outside of the study, or may choose not to receive any additional vaccinations. Participants who already received active vaccine will be asked to continue the study or can opt to receive an authorized/licensed COVID-19 vaccine outside of the study.

The safety analyses will be censored at the date of unblinding or the receipt of an unscheduled vaccinea, whichever event occurs first. SAEs and AESIs reported after unblinding or receipt of an unscheduled vaccine, whichever comes first, will be listed.

The immunogenicity analyses will be censored at the date of the receipt of an unscheduled vaccine. Immunogenicity samples taken after the receipt of an unscheduled vaccine will be included in the listings and flagged. Samples obtained from unblinded participants who do not get any further vaccination, will not be censored from the analyses.

Efficacy analyses will be censored at the date of unblinding or the receipt of an unscheduled vaccine, whichever comes first.

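### As worded, the per-protocol immunogenicity rule drops every sample from anyone infected after screening, including samples taken before the infection; it needs a date limit

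*Protocol*

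**What the plan says.** Section 9.3 defines the PPI population and then adds a sample-level exclusion: "samples obtained after missed vaccinations or from participants with natural infection occurring after screening (if applicable) will be excluded from the analysis". The synopsis repeats it, ending "from participants with natural infection occurring after screening (if applicable) will be excluded from the analysis set".

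Section 9.4.3 makes this the main immunogenicity population: "The immunogenicity analyses will be performed on the PPI population". The summaries are descriptive: "Descriptive statistics (geometric mean and 95% confidence interval, or median and interquartile range Q1-Q3, as appropriate) will be calculated for continuous immunologic parameters". The same section adds an analysis on the full analysis set (FAS), in which "participants who became infected during the study will be analyzed as a subgroup and shown in the graphs using different colors and symbols".

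Infected participants are not lost to sampling. Section 8.1.2.2 says that they "should remain on study for follow-up with assessments of safety and immunogenicity", so samples exist from both before and after the infection.

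For another intercurrent event, receipt of an unscheduled vaccine, Section 9.7.1 uses a date: "The immunogenicity analyses will be censored at the date of the receipt of an unscheduled vaccine". Section 9.8 treats the ad hoc booster as a further reason for censoring.

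**The concern.** The two limbs of the exclusion are built differently. For a missed vaccination, the sample must have been taken after the event. For infection, the sample need only come from a participant who was infected; the words about screening date the infection, not the sample. No other operative text in the protocol narrows this.

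Followed literally, the rule has three consequences. Valid pre-infection titres are discarded from groups of 30 to 75. Early geometric means are computed only in people not yet known to be infected, which is selection on a later outcome. And because Section 9.5 uses all data available at each analysis, a Day 29 or Day 85 estimate can change at a later data cut although no early sample has changed.

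The selection matters only if later infection is related to early titre. The Introduction says that a neutralising response may protect, and that the quantitative correlate has not been identified. The Amendment 15 rationale in Appendix 13 goes further and links higher responses after a second dose to better protection. If such a link holds within a regimen, the excluded people tend to be lower responders and the remaining mean is too high.

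**Working it through.** **The rule applied to one participant.** In Cohort 1a with the additional follow-up, serum for humoral immunity is drawn on Days 1, 15, 29, 57, 71, 85, 239, 422, 604 and 787 (Sections 1.3.1 and 1.3.9), 10 samples in all. Suppose a confirmed infection at about month 10, between Days 239 and 422.

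| Rule | Samples dropped | Samples kept |
|---|---|---|
| Section 9.3 as written | all 10 | 0 |
| Exclude on or after infection | Days 422, 604, 787 | Days 1 to 239 (7 samples) |

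The 7 samples that separate the two rules all precede the infection.

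**Size of the selection effect.** The plan states no figure to reproduce. The documents give no infection fraction, titre SD or titre-risk slope, so the following is an illustration on assumed values. Let y be the log10 titre at an early visit, Normal(0, SD). Let P(infected | y) = 1 − exp(−L × HR^y), with L set to give the chosen infected fraction and HR the hazard ratio per 10-fold titre. The distortion is

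ratio = 10^(E[y | not infected] − E[y]).

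| Infected | HR 1.0 (no link) | SD 0.3, HR 0.7 | SD 0.5, HR 0.5 | SD 0.5, HR 0.3 | Kept of 75 |
|---|---|---|---|---|---|
| 5% | 1.000 | 1.004 | 1.021 | 1.036 | 71 |
| 15% | 1.000 | 1.012 | 1.066 | 1.115 | 64 |
| 30% | 1.000 | 1.027 | 1.149 | 1.260 | 52 |
| 50% | 1.000 | 1.052 | 1.304 | 1.531 | 38 |

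If only samples on or after infection are excluded, an early mean keeps the people infected later, and the ratio is 1.00.

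**Precision.** Even with no link, fewer samples widen the interval on the log scale by 1/√(1 − fraction infected), if the SD is unchanged: 1/√0.85 = 1.08 at 15% and 1/√0.70 = 1.20 at 30%.

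**Timing.** Only infections known at a data cut can trigger the exclusion. At the Day 29 and Day 85 analyses that window is short. It reaches Day 787 for extended follow-up in Cohorts 1 and 3 (Section 4.1).

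**Dating silent infections.** Section 8.1.4 runs the N assay, if one can be developed, on Day 1 and then from 6 months after vaccination 2 in Cohorts 1 and 3 (Day 239). An undetected infection on Day 40 would first show at Day 239. Dating it at first seroconversion would keep Day 71 and Day 85 samples that the infection may already have boosted.

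**The case against.** The strongest reply is that nobody intended this. The exclusion speaks of samples, not participants, and the Amendment 8 log describes it as covering samples obtained after natural infection, with the participants staying in the PPI. Keeping someone in the population means little if all their samples go. This is persuasive on intent. The log is not operative text, however, and both current statements of the rule lack the time limit. The SAP is not shown and may carry a sample-level flag, but it would then depart from what the protocol fixes.

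Second, the FAS analysis is a partial check. A reader might infer that it shares the defect because "participants who became infected during the study will be analyzed as a subgroup". Section 9.4.3 does not say that these participants leave the overall FAS estimate, so that inference is not supported. The FAS is still no full substitute, because nothing there removes post-infection samples and later time points would mix vaccine and infection responses.

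Third, the Amendment 16 rationale says that the primary analysis was completed, and immunogenicity is descriptive with no hypothesis tested. Both points limit what is at stake.

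A reader might also infer large inflation. If a fraction f is infected and their geometric mean is r times that of the others, the ratio is r^(−f), which gives 3^0.2 = 1.25 at f = 20% and 3^0.3 = 1.39 at f = 30% with r = 1/3. The arithmetic is right, but r and f are assumed. In the model above, the most extreme result at 30% implies r = 1.260^(−1/0.30) = 0.46, so r = 1/3 needs a stronger link than any setting tried.

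**Conclusion.** The point stands as a wording error with a real but unquantifiable consequence. As written, Section 9.3 and the synopsis exclude pre-infection samples from the main immunogenicity analysis, unlike the date-based treatment of unscheduled vaccines and the ad hoc booster. Valid data are lost, and early geometric means are conditioned on a later outcome.

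On the assumed ranges (log10 SD 0.3 to 0.5, hazard ratio 0.3 to 0.7 per 10-fold titre), the early mean would be inflated by 0% to 4% with 5% infected, 1% to 12% with 15%, and 3% to 26% with 30%. With no titre-risk link it is zero. The effect is probably small at the Day 29 and Day 85 analyses and could grow at booster and end-of-study analyses. The Amendment 16 rationale names infections among the main reasons for the smaller remaining Cohort 2, but gives no rate.

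A reader might infer that the rule also narrows differences between dose levels or between one and two doses. That needs infection rates or titre-risk links that differ by regimen. The documents give neither, so it is not claimed. Nor is it established that low responders within a regimen are the ones infected.

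**What to change.** Reword Section 9.3 and the synopsis alike: exclude samples obtained after a missed vaccination, or on or after natural infection, and retain earlier samples. This matches the censoring in Sections 9.7 and 9.8 and the Amendment 8 description.

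Define the infection date in two parts:

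- **Molecularly confirmed infection:** the first positive molecular test or the symptom onset of the confirmed episode, whichever is earlier.
- **Infection known only from N serology:** exclude all samples taken after the last negative N result, since the infection may have occurred at any time in that interval. A first positive at Day 239 after a negative Day 1 removes everything after Day 1; a first positive at Day 422 after a negative Day 239 keeps the samples through Day 239.

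In the FAS infected subgroup, show pre-infection and post-infection samples separately.

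The cost is a short text change in two places and one sample-level flag in programming. No new data are needed. The downside is that serology-only infections still lose some samples that may have been valid, because their date is unknown.
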